8.2 Secondary Outcomes

For *secondary outcomes*, we will measure the following:

- Change in 5-chair stand test (time)
 - Measurement: time to complete 5 chair stands (seconds), post-prehabilitation minus pre-prehabilitation
 - Range: -60 to 60 seconds (higher values indicate worsening performance)
- Change in dominant handgrip strength (kg)
 - Measurement: average of 3 measurements of dominant handgrip strength, post-prehabilitation minus pre-prehabilitation
 - Range: -50 to 50 kg (higher values indicate improved performance)
- Change in protein intake (grams)
 - Measurement: 3-day average protein intake from dietary recall, post-prehabilitation minus pre-prehabilitation
 - Range: -100 to 100 grams (higher values indicate greater intake)
- Adherence to exercise
 - Measurement: proportion of days with ≥ 30 minutes of exercise out of 21-28 days per self-report
 - Range: 0-100% (higher values indicate better adherence)
- Adherence to protein intake
 - Measurement: proportion of oral nutritional supplement consumed over the total number of supplements provided per self-report

- Range: 0-100% (higher values indicate better adherence)
- Adherence to meditation
 - Measurement: proportion of days with ≥ 12 minutes of meditation out of 21-28 days per self-report
 - Range: 0-100% (higher values indicate better adherence)
- Adverse events
 - Measurement: proportion of patients who experience any adverse events per self-report
 - Range: 0-100% (higher values indicate more adverse events)

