5. STUDY POPULATION

We will review schedules to identify patients who meet the following inclusion (5.1) and exclusion criteria (5.2). A trained research assistant will perform preoperative geriatric assessment—which consists of 1) medical history (automated in EHR), 2) self-reported functional status (a questionnaire of 22 daily activities and physical tasks), 3) tests of cognitive function (Mini-Cog or MoCA test) and physical function (gait speed, chair stands, and grip strength), and 4) nutritional status (automated in EHR)—and calculate a frailty index using our EHR calculator. For eligible patients, we will explain the purpose of our study to the patients and their surgeon and ask whether they are willing to participate in 3 to 4 weeks of prehabilitation. Remote or e-consent will be obtained. Screening of potential participants will take place during the surgeon’s office visit. The assessment of eligibility will take place by telephone. Our target enrollment is 30 patients (2 patients per week for 15 weeks). See the detailed inclusion and exclusion criteria provided below:

5.1 Inclusion Criteria:

- Patient is ≥ 70 years
- Patient is ≥ 65 years old AND high risks per surgeon’s clinical judgement
- Patient is scheduled to have a gastrointestinal, gynecological oncologic, urologic, and cardiovascular procedure
- Patient provides an informed e-consent or remote consent

5.2 Exclusion Criteria:

- Surgery is scheduled less than 21 days from the expected start date of the prehabilitation intervention
- Patient is considered an inappropriate candidate per the surgeon’s assessment.
- Non-English speaking
- Patient has a major cognitive impairment, which will be defined as telephone Montreal Cognitive Assessment (MoCA) <18 or Brief Capacity Assessment Questionnaire
- Patients with chronic kidney disease stage 3 or higher will be excluded from receiving protein supplement of the prehabilitation intervention.

[figure not shown]

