6. ENROLLMENT

As stated above, patients who are scheduled to undergo a gastrointestinal, gynecological oncologic, and urologic surgery, meet inclusion criteria, and have approval from their surgeon to participate will be contacted by a study clinician who will assess eligibility, including a telephone-based preoperative frailty assessment (only patients with frailty will be eligible). This assessment includes the following domains:

- Medical history
- Self-reported functional status (activities of daily living [ADL], instrumental activities of daily living [IADL], and physical tasks without another person's help)
- Tests of cognitive function (Telephone MoCA)
- Nutritional status (BMI and self-reported weight loss)

Most of these assessments are already available or routinely collected and entered in BIDMC Online Medical Record (OMR). The study clinician will verify the existing information in OMR with the patient and fill in any missing information if needed. The OMR frailty index calculator calculates the frailty index based on information available in OMR (Figure 2). The index ranges from 0 to 1; frailty is defined as ≥ 0.25 .

Figure 2. Example report of OMR frailty index calculator and assessment report. The frailty index calculator (A) will use the latest information available in OMR to calculate a deficit-accumulation frailty index. The report shows the assessment domain-specific impairment and comparison of the frailty index against a reference population of Medicare beneficiaries.

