6.1 Baseline Assessment

Once informed e-consent or remote consent is signed, trained research personnel will administer additional measurements that are not collected as part of preoperative assessment. These measurements (provided below) may be conducted 1) during the telephone call during which informed consent is obtained; 2) during a separate call (if

requested by the patient or caregiver); 3) email survey; 4) during an in-person physical therapy session (for gait speed, chair stands, and handgrip strength); or 5) a combination of these modalities.

- Usual walking speed from 4-meter walk (if not already measured)
- Time to complete 5 chair stands (if not already measured)
- Dominant handgrip strength: average of 3 measurements (if not already measured)
- 3-day diet recall (done by telephone)
- PROMIS Profile CAT v1.0 is a 29-item, computer adaptive, patient-reported outcome measure of social roles/activities, anxiety, depression, fatigue, pain interference/intensity, physical function, and sleep disturbance domains (may be done by telephone or email)
- PROMIS v2.0 Cognition CAT is a 12-item, computer adaptive, patient-reported outcome measure of cognitive function domain (may be done by telephone)

PROMIS (available at <https://www.healthmeasures.net/index.php>) is a publicly available, validated system of highly reliable, precise measures of patient-reported health status for physical, mental, and social well-being for general population as well as people with chronic conditions. It is designed to enhance communications between clinicians and patients in diverse clinical and research settings. Computer adaptive test (CAT) allows accurate assessment with a limited number of questions from the PROMIS item bank, thereby reducing participant burden.

6.2 Medical Record Review:

Trained research personnel will obtain the following data from the OMR and record them in REDCap database:

- Demographic information: age, sex, race, ethnicity
- Chronic comorbidities
- Self-reported functional status: ADL, IADL, physical tasks by Nagi and Rosow-Breslau
- Cognitive function: telephone MOCA
- Physical function: gait speed, dominant handgrip strength, and chair stands
- Nutritional status: height, weight, BMI, weight loss in the past year, serum albumin level

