 - Range: 0-10 (higher values indicate more severe pain)
- Change in PROMIS-CAT score in Physical function (4 questions)
 - Measurement: self-reported measure of physical function
 - Range: 0-100 (higher values indicate better physical function)
- Change in PROMIS-CAT score in Sleep disturbance (4 questions)
 - Measurement: self-reported measure of sleep disturbance
 - Range: 0-100 (higher values indicate more sleep disturbance)
- Change in PROMIS-CAT score in Cognitive function (12 questions)
 - Measurement: self-reported measure of cognitive abilities
 - Range: 0-100 (higher values indicate better cognitive abilities)

The timing and modality of outcome measurements is shown in **Table 5**.

Baseline functional assessments with physical therapy staff from Hebrew SeniorLife's outpatient clinic and at the conclusion of the prehabilitation program (before surgery) will be in-person assessments (though some baseline functional assessments may be done

virtually via Zoom). In-hospital outcomes will be assessed via in-person interview or review of medical records. Postoperative assessment on post-op day 30±7 and 90±7 will be conducted via telephone interview, email survey, or medical record review.

Table 5. Timing of outcome measurement. Day 0 is defined as the date of surgery.

Outcome	Baseline functional assessment (In-person or may be done virtually)	Before surgery (In-person)	Hospitalization (In-person / medical record)	Postop Day 30±7 (Telephone / e-mail survey / medical record)	Postop Day 90±7 (Telephone / e-mail survey / medical record)
Feasibility		X			
Change in chair stands	X	X	X (if not done)*		
Change in handgrip strength	X	X	X (if not done)*		
Change in protein intake	X	X	X (if not done)*		
Adherence to exercise		X	X (if not done)*		
Adherence to protein intake		X	X (if not done)*		
Adherence to meditation		X	X (if not done)*		
Adverse events		X	X (if not done)*		
3-D CAM			X		
PQRS			X		
Surgical complications			X		
Length of stay			X		
Readmission				X	X
Death				X	X
PROMIS-CAT scores	X	X		X	X

Abbreviations: CAM, Confusion Assessment Method; PQRS, Postoperative Quality of Recovery Scale; PROMIS-CAT, Patient-Reported Outcomes Measurement Information System-Computer Assessment Test.

* We will try to measure these outcomes before surgery near the conclusion of the prehabilitation program; if not measured before surgery, we will measure them during the hospitalization.

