11. ANALYSIS PLAN

11.1 Statistical Analysis for Feasibility

We will estimate the feasibility of the entire prehabilitation program and each component; mean time for preoperative geriatric assessment; proportion of participants who enroll in the prehabilitation program; proportion of participants who drop out; and rate of missing outcome data. No statistical testing will be performed.

Sample Size Justification: We anticipate that the 3 core components of our prehabilitation program would be completed for 70% of the eligible patients⁹⁻¹⁵ (feasibility of $\geq 50\%$ would be needed for a large RCT). Assuming a 20% margin of error and a lower bound of the 95% confidence interval of 0.50, we will need 30 patients.

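### The chair-stand outcome gives no value to a participant who cannot complete 5 stands; inability should be recorded and reported as a result in its own right

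*Combined protocol and SAP*

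**What the plan says.** Section 8.2 lists change in the 5-chair stand test as a secondary outcome, measured as "time to complete 5 chair stands (seconds), post-prehabilitation minus pre-prehabilitation", and adds "Range: -60 to 60 seconds (higher values indicate worsening performance". Section 6.1 collects the baseline value in the same form: "Time to complete 5 chair stands (if not already measured".

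On the population, section 6 says that "only patients with frailty will be eligible" and that "frailty is defined as ≥ 0.25" on an index from 0 to 1. Section 5 sets the size: "Our target enrollment is 30 patients (2 patients per week for 15 weeks".

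Two places touch on absent values:
- The footnote to Table 5 (section 8.3) says of this and neighbouring outcomes that "if not measured before surgery, we will measure them during the hospitalization".
- Section 11.1 ends its list of estimates with "rate of missing outcome data. No statistical testing will be performed".

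The measure is used elsewhere too. Table 3 (section 7) lists pre/post change in chair stands under the exercise component. Section 3.1 (Aim 1) counts physical performance tests among the objective measures of adherence, and plans to estimate how much outcome data is missing.

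**The concern.** A time to complete 5 stands exists only for someone who completes them. Subtracting two such times gives a value only for people able at both visits. In a general adult sample that might rarely matter. Here entry depends on frailty, and the section 6 assessment includes physical tasks done without another person's help, so some inability is plausible.

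The loss depends on the result of the test. A participant who could not rise 5 times at baseline and can after the programme has arguably the best response the test can show. One who could and then cannot has the worst. Neither has a change value. What remains describes the fitter part of the cohort, and a reader of the pilot report could take it for the whole.

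The second consequence needs no assumption about effect size. If the form has no place for *unable*, a failed test and a test that was never arranged look the same. Aim 1's missing-data estimate is meant to inform the later randomised trial, and it would then mix a functional result with a data-collection failure.

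**Working it through.** **The plan's own figure.** The documents give no expected change, standard deviation or inability rate for chair stands. The only stated size is 30 patients, which section 11.1 derives from the primary feasibility proportion (70%, lower 95% limit 0.50). It reproduces with an exact binomial interval: 21/30 gives 0.506 to 0.853. It does not bear on this point.

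**Step 1. Who has a value under section 8.2?**

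| Baseline | After programme | Change value |
|---|---|---|
| able | able | yes |
| unable | able | none (a gain is lost) |
| able | unable | none (a loss is lost) |
| unable | unable | none |

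**Step 2. Does any other text supply a value?**
- Section 6.1 records a time only, with no code for inability and no count of stands.
- The Table 5 footnote covers a test not done before surgery, not one that was tried and failed. If the in-hospital test falls after the operation, inability becomes more likely.
- Section 11.1 has no rule for this outcome.
- The ±60 s range is not stated to be a score for inability. Neighbouring outcomes in 8.2 carry similar round limits (±50 kg, ±100 g).

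So the gap stands.

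**Step 3. How many participants?** Unknown. As an assumption only, 10% to 40% unable at one or both visits would be 0.10 × 30 = 3 to 0.40 × 30 = 12 participants without a change value. Each one counted as missing would raise the missing rate for this outcome by 1/30 = 3.3 percentage points.

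**Step 4. How far could a mean move?** The plan does not name the mean; it is used here only to gauge sensitivity. Let c be the number of both-visit completers and m their mean change, L the number going from able to unable, G the number going from unable to able, t the observed time of those who change status, and K the time assigned to inability. With 30 participants and nobody unable at both visits:

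mean over all = [c·m + (L − G)(K − t)] / 30

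Assumed t = 20 s:

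| K | m | L | G | Calculation | Result |
|---|---|---|---|---|---|
| 60 s | −1.0 | 1 | 0 | (−29 + 40)/30 | +0.37 s |
| 60 s | +1.0 | 0 | 1 | (29 − 40)/30 | −0.37 s |
| 60 s | −2.0 | 2 | 0 | (−56 + 80)/30 | +0.80 s |
| 30 s | −1.0 | 3 | 0 | (−27 + 30)/30 | +0.10 s |
| 60 s | −1.0 | 2 | 2 | −26/30 | −0.87 s (no reversal) |

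The net number of transitions k needed to reverse the sign is the smallest k with k(K − t) > (30 − k)·|m|. For t from 15 to 25 s:
- K = 60 s: 1 for a completer mean of 1 s, 2 for a mean of 2 s.
- K = 30 s: 2 to 6 for 1 s, 4 to 9 for 2 s.

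**Step 5. How the choice of summary behaves.** Take 27 participants able at baseline: 24 improve by 1.0 s and 3 go from 20 s to unable.
- Completers only: −24/24 = −1.0 s.
- Inability scored 60 s: (−24 + 3 × 40)/27 = 96/27 = +3.6 s.
- Inability scored 30 s: (−24 + 3 × 10)/27 = 6/27 = +0.2 s.
- Add 3 participants going from unable (60 s) to 20 s: (−24 + 120 − 120)/30 = −0.8 s.
- Median in the 27: −1.0 s whether or not the 3 are scored, because 24 of the 27 values are −1.0 s.

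The mean depends heavily on the assigned time and the balance of transitions, and here the median does not register the 3 losses at all. The transition counts show them directly.

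**The case against.** The strongest reply is that the plan is silent rather than wrong. Section 8.2 defines a change for each person and names no mean, and section 11.1 rules out testing. A completer-only mean is therefore something a reader supplies, and even that would be a valid, narrower quantity if labelled. This stands, and it limits what can be claimed.

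A reader might infer that the reported change will have the wrong sign. The documents do not support that. It needs transitions mostly in one direction, a small change among completers and a particular assigned time, none of which the plan gives. A reader might also take ±60 s as a scoring rule already in the plan; next to the other round limits in 8.2 it cannot be read that way.

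Three further points are fair:
- A frailty index of 0.25 or more spans history, function, cognition and nutrition. It need not mean inability to rise from a chair, and the inclusion list in 5.1 does not name frailty.
- Decline before surgery would not be wholly hidden, since handgrip strength and PROMIS physical function are also measured then.
- Section 11.1 does not define missing, so counting inability as missing is a risk, not a stated rule.

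None of this tells the study team what to record when a participant tries and fails, or cannot safely try.

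**Conclusion.** The point holds as a cheap improvement. Under the stated definition, participants unable at either visit have no value, and they are lost because of their result. The outcome then describes completers only, and the missing-data estimate may absorb some inability.

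The size and direction of the distortion are unknown. The 3 to 12 participants in the working, the 20 s times and the one-directional transitions are all assumptions. A reversal of sign is a possibility under those assumptions, not a prediction.

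A reader might infer that the decision to proceed to a randomised trial is at risk. It is not. The outcome is secondary in a single-arm pilot, the primary outcome counts sessions delivered, and the four progression criteria in section 12.4 (enrolment, feasibility, adherence, PROMIS follow-up) do not use chair stands.

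**What to change.** In section 8.2 and on the assessment form:

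1. Record *unable* (attempted and failed, or not attempted because of physical incapacity or safety) separately from *not done for logistic reasons*.
2. Report the number able at each visit and the counts going from unable to able, from able to unable, and unable at both. Present these as improved/same/worse categories, with those unable at both visits shown on their own line so that they are not read as unchanged.
3. Give the time change among participants who completed both tests, labelled as such.
4. As a supplement, give the median and interquartile range with *unable*, or any time above 60 s, scored at 60 s. State this in advance as a convention.
5. In section 11.1, say that *unable* is not missing outcome data; only tests not done for logistic reasons are.

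The cost is one extra form field and a few sentences. The downside is that 60 s is arbitrary, and participants unable at both visits score zero change under item 4, so that summary should be read only beside the counts in item 2. If nobody proves unable, nothing is lost; if inability is not recorded at the visit, it may not be recoverable later.

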- Weekly check-in calls will take place once a week for about 30 minutes per session over 3-4 weeks. During these calls the participant will talk about their goals, discuss personal motivation, and review their progress. They will be asked about any potential adverse events (such as sore muscles or falls).
- A 30 minute telephone interview will take place at the end of the intervention (in weeks 3 or 4). The participant will be asked to provide feedback discussing what parts of the

intervention worked well and what did not. We will use this information for protocol refinement.

The primary outcome is the feasibility of the prehabilitation protocol, defined as the proportion of patients to whom we can deliver an adequate dose ($\geq 50\%$ of the planned sessions) of the 3 core interventions: physical therapy ($\geq 4/8$ sessions), nutrition ($\geq 2/4$ sessions), and meditation ($\geq 2/4$ sessions). Secondary outcomes include 1) adherence to exercise, protein intake and meditation; 2) changes in 5-chair stand time, dominant handgrip strength, patient-centered outcomes, measured using PROMIS scores in physical function, cognitive function, participation in social roles/activities, depression, anxiety, sleep disturbance, pain and fatigue domains at baseline, following completion of the prehabilitation (before surgery), and on postoperative days 30 and 90; 3) clinical outcomes (3-D Confusion Assessment Method,¹ a composite complication score,² length of stay, and 30-day readmission and death); and 4) Postoperative Quality of Recovery Scale³ to be obtained around postoperative day 3; 5) adverse events.

The proposed research will provide necessary information for a larger randomized controlled trial (RCT).

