10. DATA AND SAFETY MONITORING

10.1 Adverse Events

Definition and Classification of Adverse Events

For this study, the following standard adverse event definitions are used:

- Adverse events: Any unfavorable and unintended sign, symptom, or disease temporally associated with the use of the study intervention, regardless of whether it is considered related to the study intervention.
- Serious adverse event: Any adverse event that result in death, life-threatening experience, hospitalization or prolonged hospitalization, persistent or significant disability or incapacity.
- Unanticipated problems: Any experience that 1) is unexpected in terms of nature, severity, or frequency, given the research procedures described in the protocol document and the characteristics of the study population; 2) is related or possibly related to participation in the research; 3) suggests that the research places participants or others at a greater risk of harm than was previously recognized.

Adverse events are graded according to the following scale:

- Mild: An experience that is transient and requires no special treatment. The experience does not generally interfere with usual daily activities.
- Moderate: An experience that is alleviated with simple therapeutic treatments. The experience impacts usual daily activities.
- Severe: An experience that requires therapeutic intervention. The experience interrupts usual daily activities. If hospitalization (or prolongation of hospitalization) is required for treatment, it becomes a severe adverse event.

The study uses the following adverse event attribution scale:

- Not related: The adverse event is clearly not related to the study procedures (i.e., another cause of the event is most plausible and/or a clinically plausible temporal sequence is inconsistent with the onset of the event).
- Possibly related: An event that follows a reasonable temporal sequence from the initiation of study procedures, but that could readily have been produced by a number of other factors.
- Definitively related: The adverse event is clearly related to the study procedures.

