10.2 Adverse Event Monitoring

Monitoring adverse events will be primarily performed in two ways: 1) unsolicited report from study interventionists (physical therapist, dietitian, and meditation teacher); and 2) weekly assessments by telephone using a standardized checklist.

- Unsolicited reporting: Any adverse events that occur during the in-person or virtual sessions will be assessed for severity by the study interventionists (in conjunction

with PI or an MD co-investigator). In the event of a serious adverse event, the participant or caregiver will be instructed to contact emergency medical services to receive immediate medical attention. All adverse events will be reported to the PI.

- Standardized assessment: At the beginning of cognitive behavioral intervention telephone calls, co-investigator [name] will assess adverse events using a standardized checklist that includes the following expected adverse events (see below).

Expected Adverse Events

- Exercise: fall or injury (expected risk is low); new or worsening musculoskeletal pain (expected risk is moderate); cardiovascular events including angina, arrhythmia, myocardial infarction, heart failure, or stroke (expected risk is very low); other symptoms including chest pain, dizziness/lightheadedness, dyspnea, palpitation, or syncope (expected risk is low).
- Nutrition: gastrointestinal distress such as diarrhea, nausea, constipation (expected risk is moderate); electrolyte imbalance or dehydration (expected risk is low), renal injury from increased renal solute load (expected risk is very low)³⁸ Meditation: psychological distress (expected risk is very low/rare)³⁹
- Outcome measurement: possibility of incidental finding (such as suicidal ideation) through the Patient-Reported Outcomes Measurement Information System (PROMIS) surveys (expected risk is very low)

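### The only adverse-event outcome is the proportion of patients with any event, so it may be driven by common mild events and does not change with the number of serious or related ones

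*Combined protocol and SAP*

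**What the plan says.** Section 8.2 lists adverse events as a secondary outcome with one measure: "proportion of patients who experience any adverse events per self-report". The Overview (section 2) says of the weekly calls: "They will be asked about any potential adverse events (such as sore muscles or falls").

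Section 10.1 defines an adverse event broadly; it counts "regardless of whether it is considered related to the study intervention". The same section then provides three ways to separate events:
- Seriousness: "Any adverse event that result in death, life-threatening experience, hospitalization or prolonged hospitalization, persistent or significant disability or incapacity".
- Severity: "Adverse events are graded according to the following scale" (mild, moderate, severe).
- Relatedness: "The study uses the following adverse event attribution scale" (not related, possibly related, definitively related), judged against the study procedures as a whole.

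Section 10.2 gives two sources of reports: the interventionists, and a standardized checklist at the weekly calls. It groups the expected events under exercise, nutrition, meditation and outcome measurement. Two are rated moderate: "new or worsening musculoskeletal pain (expected risk is moderate") and "gastrointestinal distress such as diarrhea, nausea, constipation (expected risk is moderate"). Cardiovascular events, including myocardial infarction, are rated very low. No percentages are given.

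Section 11.1 plans estimation without testing and does not mention adverse events. Section 10.4 includes adverse events in the monitoring report but specifies no breakdown.

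**The concern.** The outcome is one yes or no per patient. A patient with one sore muscle and a patient with a myocardial infarction add the same amount to it. The study has a single arm, so there is no control group against which to set background symptoms in frail people awaiting surgery. Attribution and grade are the main means of separating program-related harm from background, and the outcome uses neither.

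The pilot is meant to inform a larger randomized trial. Its one prespecified adverse-event figure would give that trial no rate of serious or related events during prehabilitation. Section 8.2 also limits the source to self-report, although section 10.2 collects interventionist reports, so it is unclear whether an event seen only by a therapist would count.

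**Working it through.** **1. The plan's own figure.** The only computed figure is the sample size in section 11.1: 30 patients, from 70% anticipated feasibility and a lower 95% limit of 0.50. The exact (Clopper-Pearson) interval for 21/30 is 50.6% to 85.3%, so 30 is reproduced. There is no figure for the adverse-event outcome. The calculations below use n = 30.

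**2. What is defined against what is reported.**

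| Attribute | Where defined | Used in an outcome (section 8) or analysis (section 11) |
|---|---|---|
| Seriousness | 10.1 | No |
| Severity grade | 10.1 | No |
| Attribution | 10.1 | No |
| Expected-event grouping | 10.2 | No |
| Any event, yes/no | 8.2 | Yes |

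The complication index, readmission and mortality in section 8.3 are postoperative. They do not describe harm during the 3-4 weeks of prehabilitation.

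**3. The estimate does not depend on the kind of event.** If A patients have at least one event, the outcome is A/30. Two hypothetical pilots, at two levels of A:

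| | Any event | Related serious event (exact 95% CI) |
|---|---|---|
| A = 12, all mild soreness | 12/30 = 40% | 0/30 = 0% (0% to 11.6%) |
| A = 12, of whom 3 related serious | 12/30 = 40% | 3/30 = 10% (2.1% to 26.5%) |
| A = 27, all mild soreness | 27/30 = 90% (73.5% to 97.9%) | 0/30 = 0% (0% to 11.6%) |
| A = 27, of whom 3 related serious | 27/30 = 90% (73.5% to 97.9%) | 3/30 = 10% (2.1% to 26.5%) |

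This holds at any value of A and needs no assumed event rate.

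**4. How far common events could drive the figure.** This part does need assumptions, because section 10.2 gives only words. Let each of the two moderate-risk event types occur in a proportion m of patients, each of three low-risk types in l, and each of three very-low-risk types in l/5, all independent. Then

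P(any) = 1 − (1 − m)² (1 − l)³ (1 − l/5)³.

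| m | P(any), l from 1% to 10% |
|---|---|
| 10% | 22% to 44% |
| 20% | 38% to 56% |
| 30% | 53% to 66% |
| 40% | 65% to 75% |
| 50% | 76% to 83% |
| 60% | 85% to 89% |

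An alternative is a weekly chance q of any symptom over k = 3 or 4 checks, with independent weeks: P(any) = 1 − (1 − q)^k. This gives 27% to 34% at q = 10%, 49% to 59% at 20%, 66% to 76% at 30%, and 88% to 94% at 50%. If the same patients report symptoms repeatedly, the true share is lower than this formula gives.

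The two moderate-risk types alone contribute 1 − (1 − m)²: 19% at m = 10% and 51% at m = 30%. They can make up most of the figure, but its level cannot be fixed from the documents.

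**5. What separate lines would show at n = 30.** Exact 95% intervals are 0% to 11.6% for 0/30, 0.1% to 17.2% for 1/30, 0.8% to 22.1% for 2/30, and 2.1% to 26.5% for 3/30. The chance of seeing at least one such event, 1 − (1 − p)^30, is 26% at a true rate p of 1%, 45% at 2%, 79% at 5% and 96% at 10%. The lines are informative but imprecise.

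**The case against.** The strongest reply is that one secondary outcome is not the safety plan. Under section 10.4 the principal investigator reviews serious events in real time, definitively related serious events reach the IRB within 48 hours, and a safety officer evaluates progress and risk against benefit each quarter. A pilot with three related serious events would be noticed. This stands: a reader might infer that the plan cannot describe the program's safety, and the documents do not support that. But the oversight governs conduct; it does not prespecify a result.

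Second, section 8.2 does not forbid tabulating grade or relatedness, and an estimation-only plan leaves room for listings. That is true. Still, the measure is stated, and the stated measure is the uninformative one.

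Third, a reader might infer that nearly every patient will report something, so that the outcome sits at its ceiling. The documents give no rate, and the assumed readings above run from about 22% to 89%. The plan also limits common events: exercise starts at low effort (7.1), the hyperosmolar shake is restricted to selected patients (12.2), and the checklist asks about new or worsening pain (10.2). The ceiling forecast does not stand.

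Fourth, section 10.2 groups expected events by component, but attribution in 10.1 is to study procedures as a whole. Related events by component are therefore not shown to be collected already.

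Finally, no progression criterion in section 12.4 uses adverse events, and the proposed intervals are wide; those for 0/30 and 3/30 overlap. Both points limit the consequence without removing the defect.

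**Conclusion.** The point stands in a limited form. The measure in section 8.2 cannot separate a program with only mild or unrelated events from one with serious or related events. That follows from its definition and rests on no assumed rate. That common mild events may dominate it is plausible from the moderate-risk ratings, but the extent is unknown.

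The point does not extend to the trial's safety oversight or to a claim that the proportion will be near 100%. It is worth correcting because a single-arm pilot has little else from which to report harm in the prehabilitation period. The primary outcome, the sample size and the decision to proceed are untouched.

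**What to change.** In section 8.2, report descriptively, over the adverse-event window in Table 5:
- the total number of events;
- the number and proportion of patients, with exact 95% intervals, who have (a) any serious event, (b) any moderate or severe event, and (c) any possibly or definitively related event;
- the present any-event proportion, kept as a further line.

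List event types under the exercise, nutrition and meditation headings of the section 10.2 checklist, and state that this is a grouping by type and not attribution to a component. Replace the self-report restriction so that interventionist-reported events count as well. Add the same summary to section 11, which now has none.

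The cost is a few table rows with wide intervals at n = 30, with no testing and no change in sample size. One detail needs settling: section 10.2 describes severity assessment for events during sessions but does not say who grades events found at the weekly call. The plan should name that role, so that lines (b) and (c) can be completed for every event.
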